6.3.2 Storage of Study Product(s)

Study product(s) must be stored in a safe and secure area with restricted access, under the storage conditions specified by the Sponsor (see Table 3).

6.3.3 Dispensing and Return

All study product(s) must be inventoried and a record of the dispensing for each subject must be appropriately documented. Any dispensing errors must be reported to the Sponsor/CRO and properly documented.

In the event of early termination/suspension of the clinical study, a rapid recall of study product(s) will be initiated.

Effective

Version: 6.0

Effective date: 2019-08-09 13:21

Effective

Version: 6.0

6.3.4 Treatment Compliance Management and Record

The treatment is an injection administered by the Investigator. It will be recorded in the eCRF that the injection has been administered. No other measurements of treatment compliance will be made.

6.3.5 Dose Modification

Dose modifications are not permitted.

[REDACTED]

6.4 Blinding

This is a double-blind, placebo-controlled study in which neither the Investigator, sub-Investigator, study staff, nor the subject will know the subject's study product assignment. Preparation and administration of the study products, abobotulinumtoxinA or placebo, will be completed in exactly the same way.

[REDACTED]

6.4.1 Verification of Blinding

The Sponsor's staff or designees will assess and verify maintenance of the study blind during the study through routine monitoring visits.

6.4.2 Unblinding During the Clinical Study

Emergency un-blinding during the clinical study may be required for therapeutic or for regulatory reasons (for expedited safety reporting).

A blind-break system will be available for Investigators. In such an emergency, the Investigator will only break the blind for the subject involved.

Effective date: 2019-08-09 13:21

The Investigator must notify the Sponsor immediately in the event of such an emergency (see contact details in Section 11.9. If possible, the Investigator should notify the Sponsor before breaking the blind in order to discuss this decision with the Sponsor. The Investigator is required to document each case of emergency unblinding, and inform the Sponsor immediately.

7 CLINICAL STUDY ASSESSMENT

7.1 Efficacy Assessments

7.1.1 Investigator Live Assessment using the [REDACTED] Photographic Scale of Platysmal Band Severity (ILA)

[REDACTED]

[REDACTED]

[REDACTED]

[REDACTED]

[REDACTED]

[REDACTED]

Effective

Version: 6.0

[Redacted]

[Redacted]

[Redacted]

[Redacted]

[Redacted]

[Redacted]

[Redacted]

[Redacted]

[Redacted]

[Redacted]

[Redacted]

[Redacted]

[Redacted]

Effective date: 2019-08-09 13:21

[redacted]

[redacted]

[redacted]

7.2 Safety Assessments

A safety assessment will be conducted for all subjects at the screening visit (from the informed consent signature) and at subsequent visits as outlined in the Schedule of Assessments (Table 2). Safety parameters include an evaluation of safety data by the DSMC, TEAEs, focused physical examination findings, vital signs, jawline and oral commissure safety assessment, and further targeted evaluation of remote spread of toxin effects and events suggestive of hypersensitivity like reactions will be included and reviewed throughout the course of the study.

7.2.1 Data and Safety Monitoring Committee (DSMC)

The un-blinded independent DSMC will be appointed by the Sponsor to include a minimum of three physicians with pertinent botulinum toxin expertise and a biostatistician.

The committee will review safety data after subjects [redacted] complete the Month 1 follow-up visit.

[redacted]

Effective

Version: 6.0

Effective date: 2019-08-09 13:21

[Redacted]

Evaluation of safety data for each dose group will include the following stopping criteria:

- [Redacted]
- [Redacted]

The study will discontinue enrollment if evaluation of the Month 1 safety data by the DSMC meets either of the stopping criteria, as outlined above. Further, the DSMC will review the list of AEs, including confirmed AEs of local or remote spread of toxin, to determine if there are safety findings that may result in discontinuation of study enrollment.

[Redacted]

7.2.2 Focused Physical Examination

At all visits the Investigator or designee will perform a physical examination of the subject that includes the face, head, and neck (Appendix 5).

[Redacted]

The Investigator may choose to investigate any other sign that he/she observes during the physical examination and should assess all abnormal findings for clinical significance.

At the screening and baseline visits, record clinically significant and non-clinically significant findings as medical history. Clinically significant abnormal findings at these visits are exclusionary, and the subject should not be enrolled in the study. For any clinically significant changes from the baseline visit, an AE is to be recorded.

7.2.3 Vital Signs

Vital signs will be evaluated at the baseline visit (pre and post-treatment), and at each study visit thereafter [Redacted]

Vital signs will include blood pressure, heart rate, and respiratory rate. The subject should be in a seated position and resting for at least 10 minutes prior to taking vital sign measurements.

All pre-treatment abnormal values identified as clinically significant by the Investigator, will be recorded in the medical history.

For any clinically significant changes from pre-treatment values, an AE is to be recorded.

Effective

Version: 6.0

Effective date: 2019-08-09 13:21

Effective

Version: 6.0

7.2.4 Jawline and Oral Commissure Safety Assessment

[REDACTED]

[REDACTED]

[REDACTED]

[REDACTED]

[REDACTED]

[REDACTED]

[REDACTED]

[REDACTED]

[REDACTED]

7.2.5 Adverse Events

[REDACTED]

Adverse Events are to be monitored throughout the course of the clinical trial from the time the informed consent form has been signed to the end of the subject's participation. The Sponsor should be informed if the Investigator becomes aware of any unusual safety information or any safety

Effective date: 2019-08-09 13:21

information that appears to be drug related involving a subject who has participated in a clinical study, even after a subject has completed the clinical study. All AEs are to be reported on the AE form of the eCRF with complete information as required.

If AEs occur, the main concern shall be the safety of the subjects. At the time of the ICF signature, each subject must be provided with the name and phone number of clinical trial center personnel for reporting AEs and medical emergencies.

[REDACTED]

[REDACTED]

7.2.5.1 Definitions

7.2.5.1.1 Adverse Events (AE)

According to ICH E2A, an AE is any untoward medical occurrence in a patient or a clinical investigation subject administered a pharmaceutical product and which does not necessarily have a causal relationship with this treatment. An AE can therefore be any unfavorable and unintended sign (including an abnormal laboratory finding), symptom, or disease temporally associated with the use of a medicinal (investigational) product, whether or not related to the medicinal (investigational) product.

Thus any new sign, symptom or disease, or any clinically significant worsening of an existing sign, symptom or disease (including new episodes of a chronic disease [e.g., hay fever, allergy]) compared to the condition at the first visit, should be considered as an AE. Lack of efficacy is not considered as an AE.

Notes:

- There should be an attempt to report a diagnosis rather than the signs, symptoms or abnormal laboratory values associated with the report of an AE. However, a diagnosis should be reported only if, in the investigator's judgment, it is relatively certain. Otherwise, symptoms, signs, or laboratory values should be used to describe the AE.
- Pregnancy is not to be considered as an AE; however, is a special situation that must be monitored as described in Section 7.2.5.2.4.

[REDACTED]

Effective

Version: 6.0

Effective date: 2019-08-09 13:21

7.2.5.1.2 *Treatment Emergent Adverse Event (TEAE)*

A TEAE is an event that emerges during treatment, having been absent pre-treatment, or worsens relative to the pretreatment state.

Investigators are responsible for monitoring, recording, and reporting all AEs that occur during the study as described. TEAEs will be delineated from AEs following database lock.

7.2.5.1.3 *Serious Adverse Events (SAE)*

A SAE is any untoward medical occurrence that at any dose:

- Results in death,
- Is life-threatening,
- Requires inpatient hospitalization or prolongation of existing hospitalization,
- Results in persistent or significant disability/incapacity, or
- Is a congenital anomaly/birth defect.

Important medical events that may not result in death, be life-threatening, or require hospitalization may be considered an SAE when, based upon appropriate medical judgment, they may jeopardize the safety of the subject, and may require medical or surgical intervention to prevent one of the outcomes listed in this definition. Examples of such events are intensive treatment in an emergency room or at home for allergic bronchospasm, blood dyscrasia, or convulsions that do not result in hospitalization.

Note: The term “life-threatening” refers to an event in which the subject was at risk of death at the time of the event; it does not refer to an event which hypothetically might have caused death if it were more severe.

Inpatient hospitalization is considered to have occurred if the subject has had to stay for a night at the hospital. The criterion for prolongation of hospitalization is also defined as an extra night at the hospital. Hospitalization may not constitute sufficient grounds to be considered as an SAE if it is solely for the purpose of a diagnostic test(s) (even if related to an AE), elective hospitalization for an intervention that was already planned before subject enrolment in the clinical study, admission to a day-care facility, social admission (e.g., if the subject has no place to sleep), or administrative admission (e.g., for a yearly examination).

7.2.5.1.4 *Unexpected Adverse Drug Reaction*

An unexpected adverse drug reaction is defined as an adverse reaction, the nature or severity of which is not consistent with the applicable study product information (e.g., Investigator’s Brochure for an unapproved investigational product or the medicinal package insert/summary of product characteristics for an approved investigational product).

Effective

Version: 6.0

Effective date: 2019-08-09 13:21

Effective

Version: 6.0

7.2.5.1.5 *Adverse Event Reporting Period*

The clinical study period during which AEs must be reported is the period from when the subject signed the ICF to the end of the subject’s participation.

The Sponsor should be informed if the Investigator becomes aware of any unusual safety information or any safety information that appears to be drug-related involving a subject who has participated in a clinical study, even after a subject has completed the clinical study.

7.2.5.1.6 *Severity*

Severity is a clinical determination of the intensity of an AE and not the severity of a disease.

The Investigator is to classify the intensity of AEs using the following definitions as a guideline. For this classification, the Investigator will take into account the possible range of the intensity of the event and report the grade of intensity which is the most appropriate according to his/her medical judgment.

Mild	Awareness of signs or symptom, but easily tolerated.
Moderate	Discomfort, enough to cause interference with usual activity.
Severe	Incapacitating with inability to work or perform usual activity.

7.2.5.1.7 *Relationship to the Study Product and/or Clinical Study Procedure*

The Investigator is to determine whether there is a reasonable causal relationship between the occurrence of the AE and exposure to the study product and/or clinical study procedure.

Medical judgment should be used to determine the relationship, considering all relevant factors including the pattern of reaction, temporal relationships, relevant medical history, and confounding factors such as co-medication or concurrent diseases.

The expression “reasonable causal relationship” is meant to convey in general that there are facts or arguments to suggest a causal relationship (ICH E2A, Section IIIA 1).

The relationship assessment for an AE is to be completed using the following definitions as a guideline:

Reasonable Possibility:

According to the reporting Investigator, there is a reasonable possibility (i.e., suggestive evidence or arguments) that there is a causal relationship irrespective of the dose administered between:

- The study product (active or placebo) and the AE.
- The clinical study protocol procedure (e.g., bruising or marks from blood draws, injection related trauma, etc.) and the AE.

A two-point scale (Yes or No response) shall be used for the causality assessment. The Investigator shall be asked to indicate a response to each of the following questions in the eCRF:

Effective date: 2019-08-09 13:21

Effective

Version: 6.0

- “Do you consider that there is a reasonable possibility that the event may have been caused by the study product?”, and
- “Do you consider that there is a reasonable possibility that the event may have been caused by the study product injection procedure?”

If any of these questions is answered Yes, the AE is considered related.

No Reasonable Possibility:

No suggestive evidence or arguments can be identified regarding a causal relationship between the study product or the clinical study protocol procedure and the AE.

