1.6 Safety Endpoints

Safety endpoints include:

(i) Treatment Emergent Adverse Events (TEAEs)

Adverse events (AEs) are to be monitored throughout the course of the study. The study period for the purpose of AE collection is defined as the period from the signing of a study specific informed consent to study exit for a subject. AEs recorded on the electronic case report forms (eCRFs) will be coded using the Medical Dictionary for Regulatory Activities (MedDRA). AEs will be classified as treatment-emergent adverse events (TEAEs) if the AE had an onset time greater than or equal to the time of the dose of study treatment.

Adverse events endpoints include:

- Incidence,
- Causality (related/not related to investigational product or protocol procedure),
- Intensity (mild/moderate/severe),
- Time to onset,
- Duration,
- Leading to study withdrawal,
- Seriousness.

(ii) Focused Physical Examination

At all visits the Investigator or designee will perform a physical examination of the subject that includes the face, head, and neck. The Investigator may choose to investigate any other sign that he/she observes during the physical examination and should assess all abnormal findings for clinical significance.

(iii) Vital Signs

Vital signs (including blood pressure, heart rate, and respiratory rate) will be evaluated at the baseline visit (pre and post-treatment), and at each study visit thereafter through the termination visit.

Vital signs endpoints include:

- Values,
- Changes from baseline.

All abnormal values at the screening visit identified as clinically significant by the Investigator will be recorded in the medical history.

For any clinically significant changes from the screening visit, an AE is to be recorded.

Normal ranges checks, as programmed in the eCRF to alert the investigator to assess clinical significance for values outside of these ranges, are shown in Table 4 below.

Title
43USD1804 Statistical analysis plan Doc id GALDERMA

Table 4. Vital Sign Normal Ranges

Measure	Normal Range
Sitting Systolic blood pressure	90-150 mmHg
Sitting Diastolic blood pressure	60-90 mmHg
Sitting Heart rate	50-100 beats/min
Sitting Respiratory rate	12-24 breaths/min

(iv) **Jawline and Oral Commissure Safety Assessment**

To determine if treatment with abobotulinumtoxinA or placebo of the platysmal bands adversely affects the subject's jawline or oral commissures, the Investigator will assess these areas relative to the subject's pre-treatment appearance

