2.1.2 Reporting Conventions

The formats for the tables, listings, and figures described in this SAP will be provided in a companion document. Changes to the formats of these reports that are decided after the finalization of the SAP will not require an amendment. In addition, any additional supportive or exploratory analyses requested after SAP approval will not require amendment of the SAP. These additional analyses will be described in the CSR.

All study data from the eCRFs as well as derived variables will be provided in subject data listings. An indication of specific listings for each data type will not be indicated in the text of subsequent SAP sections. Data listings supplied as part of the CSR will be sorted by treatment group, study center number concatenated with subject number, assessment dates, and/or time point.

The following conventions will be applied to all data presentations and analyses:

- Placebo-treated subjects will be pooled together in summary tables and for analyses.
- Treatment groups to be summarized include abobotulinumtoxinA and pooled placebo.
- Quantitative variables will generally be summarized by the number of subjects, mean, standard deviation, median, minimum, and maximum. Unless otherwise specified, the minimum and maximum values will be displayed to the same number of decimal places as the raw data, the mean and median will be presented to one extra decimal place compared to

GALDERMA

Title

43USD1804 Statistical analysis plan -

the raw data, and the standard deviation will be displayed to two extra decimal places compared to the raw data.

- Categorical variables will be summarized by the number and percentage of subjects within each category. Unless otherwise specified, the percentage will be presented in parentheses to one decimal place. Frequency and percentage values of 0 will be presented as '0' rather than '0 (0)'.
- All summary tables will include the analysis population sample size (i.e., number of subjects) in each treatment group.
- Date variables will be formatted as DDMMMYYYY for presentation.

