2.5.2 Adverse Events

An overall summary of all AEs will be provided by treatment group, which will include:

- number and percentage of subjects with at least one AE and number of events,
- number and percentage of subjects with at least one TEAE and number of events,
- number and percentage of subjects with at least one related TEAE and number of events,

GALDERMA
Title
43USD1804 Statistical analysis plan

- number and percentage of subjects with at least one mild, moderate, and severe TEAE and number of events,
- number and percentage of subjects with at least one TEAE leading to discontinuation and number of events,
- number and percentage of subjects with at least one serious TEAE and number of events.

All TEAEs, serious TEAEs, TEAEs by maximum intensity, TEAEs by causality, TEAEs by maximum intensity and causality, related TEAEs, and TEAEs leading to discontinuation will be summarized by treatment group, SOC, and PT including number of subjects with at least one event, percentages, and number of events.

For related AEs, the number of days to onset and duration of event will be summarized by treatment group, SOC, and PT.

Time to onset of an AE will be derived as the start date minus the date of treatment. If the start date is missing, it will be assumed that the AE started on the day of treatment.

Duration of an AE will be derived as the stop date minus the start date + 1. If the start date is missing, it will be assumed that the AE started on the day of treatment. Missing stop date will not be imputed and therefore no duration will be calculated in these cases.

For subject counts, a subject will only be counted once per SOC and once per PT in cases where multiple events are reported for a subject within SOC or PT. For event counts, subjects with multiple events in a category will be counted for each event.

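### Related TEAEs combine study-product and injection-procedure causality, which weakens the active-placebo contrast in the aggregate related rows; separate rows can be added from data already collected (minor)

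*Protocol*

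**What the plan says.** Protocol 7.2.5.1.7 puts two separate Yes/No questions in the eCRF. The first asks about a "reasonable possibility that the event may have been caused by the study product". The second asks whether "the event may have been caused by the study product injection procedure". The same section then sets the rule: "If any of these questions is answered Yes, the AE is considered related".

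SAP 1.6(i) carries the merge into the analysis as one endpoint: "Causality (related/not related to investigational product or protocol procedure". SAP 2.5.2 builds on it in three places:

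- Overall summary: "number and percentage of subjects with at least one related TEAE and number of events".
- SOC and PT tables: "TEAEs by maximum intensity and causality, related TEAEs, and TEAEs leading to discontinuation will be summarized by treatment group, SOC, and PT".
- Timing: "For related AEs, the number of days to onset and duration of event will be summarized by treatment group, SOC, and PT".

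The individual answers survive in the listings, under SAP 2.1.2: "All study data from the eCRFs as well as derived variables will be provided in subject data listings".

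Three other provisions matter here. Protocol 6.4 has active and placebo prepared and administered identically. SAP 2.1.2 pools the placebo subjects. SAP 2.5 plans no inferential analysis of safety.

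**The concern.** This is a dose-ranging study, so a reader of the safety tables will want to know how often investigators attributed events to the drug, by dose and against placebo. The eCRF collects that answer, but the visible tables do not display it.

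The related category also takes in events caused by the needle. Protocol 7.2.5.1.7 itself gives injection trauma as an example of a procedure-related event. Every subject is injected, so such events should appear under placebo as well as active treatment. A background common to the arms moves the related-TEAE rates closer together in relative terms and makes their difference noisier. In the onset and duration tables, a row that holds both causes averages two processes that may have different timing.

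The any-related-TEAE row is one of only a few lines in the overall AE summary. Safety here is descriptive, so the choice of what to display is in effect the analysis.

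**Working it through.** **Group sizes.** Protocol 5.1 gives three groups, each with 60 active and 20 placebo subjects: 3 x (60 + 20) = 240, which reproduces the planned enrolment. With placebo pooled, each dose compares 60 subjects with 60. The visible text gives no adverse event rates, so all rates below are assumptions.

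**Formula.** Let d be the incidence of product-related events and q the incidence of procedure-related events. Take q as equal in the two arms and independent of product events. The proportion with at least one related event is then 1 - (1 - d)(1 - q), and the difference between arms is

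(1 - q) x (d_active - d_placebo).

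For example, with d = 10% (6 of 60) v 1.7% (1 of 60) and q = 20%: active 1 - 0.900 x 0.80 = 28.0%, placebo 1 - 0.983 x 0.80 = 21.3%, difference 6.7 points.

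| Assumed d, active v placebo | q | Merged rate, active v placebo | Difference (points) | Ratio |
|---|---|---|---|---|
| 10% v 1.7% | 0 | 10.0% v 1.7% | 8.3 | 6.0 |
| | 20% | 28.0% v 21.3% | 6.7 | 1.31 |
| | 30% | 37.0% v 31.2% | 5.8 | 1.19 |
| 15% v 2% | 0 | 15.0% v 2.0% | 13.0 | 7.5 |
| | 10% | 23.5% v 11.8% | 11.7 | 1.99 |
| | 40% | 49.0% v 41.2% | 7.8 | 1.19 |
| 20% v 5% | 0 | 20.0% v 5.0% | 15.0 | 4.0 |
| | 10% | 28.0% v 14.5% | 13.5 | 1.93 |
| | 40% | 52.0% v 43.0% | 9.0 | 1.21 |

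The q = 0 rows are what a product-related row would show.

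**Precision.** The standard error of the difference is the square root of the sum of p(1 - p)/60 over the two arms. For 15% v 2% it rises from 5.0 points at q = 0 to 8.0 at q = 20% and 9.1 at q = 40%.

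**Independence.** The shrinkage comes from subjects who have both kinds of event. Take 10% v 1.7% with q = 20%. If no subject had both, the merged rates would be 30.0% v 21.7%: the difference stays at 8.3 points, although the ratio still falls to 1.38. If every subject with a product event also had a procedure event, both arms would show 20% and the difference would vanish. Independence lies between these extremes.

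**Reach.** A PT row is diluted only if that same term arises from both causes. An SOC row is diluted if it gathers terms of both kinds. The overall related row always combines them.

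**Which procedure.** The causality guidance in Protocol 7.2.5.1.7 refers to study procedures in general, with blood draws among its examples, and SAP 1.6(i) refers to protocol procedures. The eCRF question covers only the injection. Protocol 7.2.5.2.1, listing what the AE form records, names only the relationship to the study product.

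**The case against.** The strongest reply is that little is hidden. SAP 2.5.2 tabulates all TEAEs by SOC and PT, and needle effects such as bruising will usually code to other terms than a toxin effect. Remote-spread and hypersensitivity events are found by a PT list and a standard query followed by medical review (SAP 2.5.3), not by the related flag. Jawline and commissure findings have their own summary. The safety endpoints in Protocol 2.1.4 lead with the incidence and severity of TEAEs, whatever their cause. All of this stands, and it confines the point to the aggregate related rows, the mixed SOC or PT rows, and the onset and duration tables.

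It can also be said that TEAEs by causality might already be split, since the table formats are in a companion document and parts of the SAP text are not visible. That cannot be excluded, but the visible definition in SAP 1.6(i) is two-level and matches the protocol's merging rule.

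A third argument favours the merged category: it is inclusive. A blinded investigator may attribute a true drug effect to the needle, and the combined row still counts it. This also stands, and it is why the combined category should remain. A reader might infer that the dose comparison should rest on the product-related rows. The documents do not support that step, because those rows depend on attribution, whereas the comparison of all TEAEs by randomised arm does not.

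Finally, the listings keep both answers. That preserves the information, but the reader would have to count by hand across about 240 subjects.

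**Conclusion.** The point holds as a minor reporting weakness. The merge is a stated rule, and the visible tables follow it throughout.

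The direction of the effect on the ratio is arithmetic, but its size rests on assumed rates. With q equal and independent, the risk difference in the any-related row loses the fraction q of its value. In the first scenario that means 8.3 points becoming 6.7 or 5.8. The ratios look more dramatic mainly because the assumed placebo rate is very low (1 in 60 in that scenario), so the difference is the fairer scale.

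A reader might infer that the plan conceals a dose-related safety signal. The documents do not support that. The PT-level tables of all TEAEs, the events of special interest, the jawline and commissure summary and the listings keep a product effect visible. No safety test is planned, so no error rate or power changes.

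Nor can it be said that the merge flattens a trend across doses. Identical administration is stated for active against placebo, but the injection details by dose group are redacted, so equality of q across doses cannot be checked. If q does differ, the combined row mixes procedure and product differences, and separate rows help there too.

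**What to change.** In SAP 1.6(i) and 2.5.2:

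- Keep the combined related category as defined.
- Add product-related and injection-procedure-related rows, taken directly from the two eCRF answers, to the overall AE summary, the related-TEAE tables by SOC and PT, and the onset and duration tables. An event with Yes to both questions counts in both rows.
- State that the comparison of all TEAEs by arm remains the main safety comparison, and that the product-related rows are supportive because they depend on investigator attribution.
- Reconcile the procedure wording in Protocol 7.2.5.1.7 and SAP 1.6(i) with the narrower eCRF question, and align the AE form description in Protocol 7.2.5.2.1 with the two answers collected.

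The cost is a few extra rows or columns. Both answers are already collected and study conduct does not change. SAP 2.1 provides for amendment before database lock, and it allows supportive analyses to be added without one if they are described in the study report.
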